## **9.6 Reporting Pregnancies**

Pregnancy itself is not considered an AE or SAE (unless there is a suspicion that the IMP may have interfered with the effectiveness of a contraceptive medication). Pregnancy is an important medical event that must be followed up. Any pregnancy that occurs during the clinical trial where the fetus could have been exposed to IMP must be followed through the outcome of the pregnancy.

It is the responsibility of the Investigator to obtain the outcome and condition of the infant information within 30 calendar days after the initial notification and approximately 30 calendar days postpartum.

If a subject or investigator suspects that the subject may be pregnant prior to IMP administration, the IMP must be withheld until the results of pregnancy testing are available. If pregnancy is confirmed, the subject must not receive IMP and must not be enrolled in the trial. If pregnancy is suspected while the subject is receiving IMP treatment, the IMP must immediately be withheld until the result of pregnancy testing is known.

If a female reports a pregnancy or has a positive pregnancy test during the trial, then the subject should be discontinued from the study and the investigator must report the pregnancy and the outcome of the pregnancy to the CRO Drug Safety Navigator Associate within 24 hours of learning about the pregnancy.

A Pregnancy Reporting Form will be completed by the trial site's principal investigator and sent to CRO Drug Safety Navigator (*see SMP*). The CRO Drug Safety Navigator will forward the documentation to the medical monitor and the sponsor for review.

At the completion of the pregnancy, the Pregnancy Outcome Form is to be submitted to the CRO Drug Safety Navigator via the SAE contact details. The CRO Drug Safety Navigator will manage the query and reconciliation process until the pregnancy documentation is complete.

## **10 STATISTICAL HYPOTHESES AND METHODS OF ANALYSES**

### **10.1 Analysis Populations**

The following analysis populations will be considered:

Safety Set (SAF) – The SAF includes all enrolled subjects who have received at least one dose of the investigational product in this study. The SAF will be analyzed for all assessments. Subjects in the SAF will be analyzed as treated.

The statistical analysis of baseline, and primary/secondary endpoint data will be performed for the SAF.

Data will be summarized by treatment group as received in NVU-003 and overall. Group 1 and group 2 consist of subsets of subjects who received masked treatment with NOV03 or saline, respectively, in NVU-003.

### **10.2 Statistical Hypotheses**

There are no formal hypotheses to be tested in this open-label safety extension trial.

### **10.3 Sample Size**

Approximately 200 subjects will be enrolled in order to ensure that at least 100 evaluable subjects complete the week 26 treatment period and at least 100 evaluable subjects complete the week 52 treatment period.

With 100 subjects completing the week 52 (or week 26) treatment period, the study will have 95% or greater chance of observing adverse events that occur at a true incident rate of 3.0% or higher.

### **10.4 Statistical Analysis**

#### **10.4.1 General Considerations**

Quantitative variables will be summarized using number of subjects (n), mean, median, standard deviation, minimum and maximum. Qualitative variables will be summarized using counts and percentages.

Summaries will be provided for demographics, medical history, concurrent therapies, and subject disposition.

For the purpose of summarization, medical history, concurrent therapies, and AEs will be coded to MedDRA and WHO Drug dictionaries, as appropriate.

Presentation will be by treatment group for subjects treated with NOV03 in NVU-003 and subjects treated with the saline comparator in NVU-003 as well as overall.

The results of assessments performed at multiple visits will be presented by visit as appropriate unless otherwise specified.

The results of bilateral ocular assessments will be summarized separately for study and fellow eyes.

Baseline measures are defined as the measure prior to the administration of IMP in the double masked trial NVU-003, e.g. baseline in NVU-003 and NVU-004 are identical. CFB will be calculated as Value at Follow-up Visit – Value at Baseline Visit.

#### 10.4.2 Unit of Analysis

For efficacy endpoints, the unit of analysis will be the study eye which was determined during NVU-003. This information will be transferred to this NVU-004 trial.

#### 10.4.3 Missing Data

The primary analysis will be completed on the SAF with available data per subject.

#### 10.4.4 Multiplicity Considerations

This section is not applicable.

#### 10.4.5 Primary Safety Analyses

All safety analyses will be performed on the Safety Population.

Dosing information will be summarized overall and by treatment from NVU-003 and listed for each subject. Discontinuation of treatment will be summarized. The primary reason for IMP discontinuation will also be summarized by treatment group as received in NVU-003. Adverse events (AEs) will be coded using the MedDRA dictionary. An AE will be defined as treatment emergent if it occurs or worsens after the first dose of trial treatment in clinical trial NVU-004.

Frequencies and percentages of subjects with TEAEs, treatment related TEAEs, serious TEAEs, and TEAEs causing premature discontinuation will be provided. Furthermore, frequencies will be given of subjects with TEAEs by system organ class; by system organ class and preferred term; by system organ class, preferred term and maximal severity; by system organ class, preferred term and strongest relationship; and by system organ class, preferred term, maximal severity, and strongest relationship. Separate summaries will be provided for ocular and non-ocular AEs. Ocular AEs will be summarized at the subject level, at the eye level, and separately for study and fellow eyes.

The treatment groups as assigned in NVU-003 will be compared descriptively with regard to safety endpoints. No inferential comparison will be conducted.

Concomitant medications will be coded using the most recent version of WHO-Drug Dictionary.

#### 10.4.6 Secondary Safety Analyses

Other safety endpoints including visual acuity, slit-lamp biomicroscopy, dilated funduscopy, and intraocular pressure will be summarized by visit and by treatment group as received in NVU-003 using descriptive statistics. Changes from baseline (baseline as defined in clinical trial NVU-003) will also be summarized where appropriate. For assessments performed by eye, study eye and fellow eye will be summarized separately.

#### 10.4.7 Other Pre-specified Efficacy Analyses

The analysis of other pre-specified efficacy endpoints will use the SAF with available data per subject.

Quantitative other pre-specified efficacy endpoints will be summarized descriptively (n, mean, standard deviation, median, min, and max) by visit and by treatment group as assigned in NVU-003.

Dichotomous other pre-specified efficacy endpoints will be summarized descriptively (frequency and percentage).

#### 10.4.8 Exploratory Analyses

Exploratory endpoints MGD score, Schirmer's Test I, and TFBUT will be summarized descriptively.

#### 10.4.9 Ocular Comfort and Acceptability Analyses

Eyedrop comfort and acceptability will be assessed on the SAF population with available data per subject. The data will be summarized descriptively.

#### 10.4.10 Interim Analyses

An interim safety analysis is planned for the first 100 subjects completing 26 weeks treatment with IMP including all assessments of Visit 4. This 26-week interim report will be used to submit the initial NDA. The safety analyses will be identical to the final analyses after 52 weeks of treatment with IMP including Visit 6 (52 weeks).

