#### 4.6 Justification of Trial Design

This 52-week open-label extension trial will enroll subjects successfully completing trial NVU-003. The open-label single-arm treatment design is deemed adequate for investigating long-term safety/tolerability of NOV03 QID at regular intervals in at least 100 subjects in long term (52-week), day to day use. An interim analysis will be performed after 100 subjects complete 26-weeks of treatment.

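### Section 10.4.10 words the NDA-supporting interim safety analysis as a week-26 completer set, which conflicts with the all-dosed Safety Set rule in Sections 10.1 and 10.4.5 and leaves the analysis set and data cut-off unsettled

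*Combined protocol and SAP*

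**What the plan says.** Section 10.4.10 is the only section that specifies the interim. It says: "An interim safety analysis is planned for the first 100 subjects completing 26 weeks treatment with IMP including all assessments of Visit 4". It gives the purpose ("This 26-week interim report will be used to submit the initial NDA") and the method ("The safety analyses will be identical to the final analyses after 52 weeks of treatment with IMP"). It names neither an analysis set nor a data cut-off date.

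The general rules are in three other places:

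- Section 10.4.5: "All safety analyses will be performed on the Safety Population". No exception is made for the interim.
- Section 10.1: "The SAF includes all enrolled subjects who have received at least one dose of the investigational product in this study". Completion is not required.
- Section 10.4.3: "The primary analysis will be completed on the SAF with available data per subject".

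Section 4.6 describes the interim differently, as an event in time: "An interim analysis will be performed after 100 subjects complete 26-weeks of treatment".

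Section 10.4.5 also lists outputs about stopping treatment: a summary of treatment discontinuation, the frequency of TEAEs that led to premature discontinuation, and this one: "The primary reason for IMP discontinuation will also be summarized by treatment group as received in NVU-003".

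**The concern.** An analysis that is for the first 100 subjects to complete 26 weeks selects people, and it selects them on an outcome: still being on treatment at week 26. Anyone who stopped earlier, including anyone who stopped because of an adverse event, cannot be in the set. The Safety Set selects only on having been dosed. Both rules cannot govern the same report. A programmer working from Section 10.4.10 and one working from Section 10.4.5 would use different denominators.

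Adverse events are the primary endpoint (Section 6.1), the primary objective is safety and tolerability (Section 3.1), and this is the report that goes into the initial NDA. Stopping because of an adverse event is a central tolerability signal. It is the signal that a completer set cannot show.

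**Working it through.** **1. The plan's own figure.** Section 10.3 claims at least a 95% chance of observing an adverse event with a true rate of 3.0% among 100 completers. 1 − 0.97^100 = 0.9524, so the figure reproduces. The question is which subjects are analysed; the detection statement is not in doubt.

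**2. The two readings.**

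| | Completer set | Timing trigger |
|---|---|---|
| Supported by | The sentence in 10.4.10 that assigns the analysis to the first 100 completers | 4.6; 10.4.5; 10.1; 10.4.3; the identical-analyses sentence in 10.4.10 |
| Subjects analysed | 100 | All dosed by the cut-off |
| Stopped before week 26 | 0, by definition | As observed |
| TEAEs causing a stop before week 26 | 0, by definition | As observed |

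The zeros follow from the definition of a completer and need no assumed withdrawal rate.

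**3. How many early stoppers a completer set would omit.**

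From the documents: 200 enrolled and at least 100 completers at both week 26 and week 52 (10.3); no replacement after dosing (5.5); 18 months from first visit to last visit (8.8); 52 weeks per subject.

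Enrolment window: 18 months = 78.3 weeks; 78.3 − 52 = 26.3, taken as 26 weeks.

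Assumptions: uniform accrual, a constant withdrawal hazard λ, and a proportion w withdrawn by week 26, so λ = −ln(1 − w)/26. The documents give no value for w.

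- Time of the 100th completer: T = 26 + 13/(1 − w) weeks. This is after week 26 of the trial, so all 200 are dosed by then.
- Subjects enrolled at least 26 weeks before T: 100/(1 − w). Of these, 100 complete and 100w/(1 − w) have stopped.
- The remaining R = 200 − 100/(1 − w) subjects were enrolled between T − 26 and 26 weeks before T. Their mean probability of still being on treatment is m = [exp(−λ(T − 26)) − (1 − w)] / [λ(52 − T)].
- Early stoppers = 100w/(1 − w) + R(1 − m).

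Example, w = 0.20: T = 26 + 13/0.8 = 42.25; λ = 0.00858; first term 25.0; R = 75; m = (0.8698 − 0.8)/(0.00858 × 9.75) = 0.834; second term 75 × 0.166 = 12.4; total 37.4.

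Largest w that fits the plan: 100 of 200 must also complete week 52. Under a constant hazard, (1 − w)² ≥ 0.5, so w ≤ 1 − √0.5 = 29.3%.

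| Assumed w | T (weeks) | Early stoppers | Share of 200 | Not yet at week 26 |
|---|---|---|---|---|
| 0% | 39.0 | 0 | 0% | 100 |
| 10% | 40.4 | 18.1 | 9.0% | 81.9 |
| 20% | 42.3 | 37.4 | 18.7% | 62.6 |
| 29.3% (plan's limit) | 44.4 | 56.4 | 28.2% | 43.6 |
| 30% | 44.6 | 57.9 | 28.9% | 42.1 |

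The last column is a separate group. Those subjects have shorter follow-up and were not selected out by stopping.

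**4. Sensitivity to the enrolment period.** For enrolment over 13 to 52 weeks, the 10 / 20 / 30% counts become 16–19 / 35–39 / 56–59, and the count at the plan's limit becomes 54–58. All 200 are still dosed by T.

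**The case against.** The strongest reply is that the population is settled elsewhere and that only the wording of one sentence points to completers. Section 10.4.5 makes no exception for the interim, and Section 10.1 has no completion condition. Section 4.6 plainly uses the 100 completers as timing. If the interim analyses are identical to the final ones, the population carries over as well as the tables. A requirement for discontinuation tables is itself a sign that nobody meant to restrict the set to completers. This has weight, and it makes the trigger reading the more likely intention. It does not remove the conflict, because the completer wording stands in the one section that specifies the interim, and no cut-off is given there. Section 10.5 mentions formal analysis plans for the study. One of these may resolve the point, but the supplied text does not.

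It is also fair to say that the consequences are limited. There are no hypotheses (10.2) and Section 10.4.10 sets no decision rule. Early-termination data are collected (8.4.2), serious events are reported within 24 hours (9.3.1), and the final Safety Set analysis is untouched.

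Three stronger readings are tempting and are not supported:

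- **That the interim will exclude dropouts.** The plan does not commit to this; several passages point the other way.
- **That up to 100 early stoppers could be missing, because 200 are enrolled to secure 100 completers.** A 50% loss by week 26 meets the week-52 target only if nobody leaves in the second half of the year. Under the constant hazard used here, the limit is 29.3% and about 56 subjects.
- **That the interim TEAE percentages would be too low.** If early stoppers have the same TEAE rate as completers, the percentage does not change. The documents give no basis for the sign or size of a difference.

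**Conclusion.** The concern holds in a conditional form. Section 10.4.10, read literally, conflicts with Sections 10.1 and 10.4.5, and the text supplied neither resolves the conflict nor states a data cut-off. The trigger reading is better supported; if it is what the sponsor intends, the harm is an unclear rule and nothing more.

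If the literal wording is followed, the report used for the NDA shows no discontinuation and no TEAE-related discontinuation before week 26, whatever happened, and it omits every other TEAE in those subjects. At assumed week-26 withdrawal of 0 / 10 / 20 / 30%, about 0 / 18 / 37 / 58 early stoppers are left out; at the limit set by the plan's week-52 target the number is about 56. These counts rest on 200 dosed, uniform 26-week accrual and a constant hazard, none of which is guaranteed. The zeros do not depend on these assumptions.

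This should be fixed before the interim data cut. The final analysis and the Section 10.3 detection statement need no change.

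**What to change.** Reword Section 10.4.10 along these lines: *The 100th subject completing Visit 4 triggers the interim data cut-off. The interim analysis includes all SAF subjects dosed by the cut-off, including early discontinuations and ongoing subjects, with all data to that date.* Report exposure and the number who have completed week 26 alongside the safety tables. A separate table for week-26 completers, or exposure-adjusted rates, can be added as support. Section 4.6 already agrees with this wording and needs no change.

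The cost is one wording change and a cut-off rule, with no extra subjects or visits. There are two downsides. The records of early stoppers and ongoing subjects must also be cleaned at the cut. Crude percentages will mix exposure lengths (with no withdrawal and uniform accrual, 39 − 26 = 13 weeks to 39 − 0 = 39 weeks), which can lower crude rates; this is why exposure should be reported. If the sponsor already intends the Safety Set, the edit changes no analysis.

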## **10.5 Additional Analyses**

Additional analysis of study measures, combining / pooling data with trial NVU-003 and / or NVU-002 might be described in a statistical analysis plan, separate from the formal study statistical analysis plans.

## **11 COMPLIANCE WITH GOOD CLINICAL PRACTICES, ETHICAL CONSIDERATIONS, AND ADMINISTRATIVE ISSUES**

This trial will be conducted in compliance with the protocol, Good Clinical Practices (GCPs), including the International Conference on Harmonization (ICH) Guidelines, and in general, consistent with the Declaration of Helsinki. In addition, all applicable local, state, and federal requirements relevant to the use of IMPs in the countries involved will be adhered to.

### **11.1 Protection of Human Subjects**

#### **11.1.1 Subject Informed Consent**

Informed consent/assent must take place before any trial specific procedures are initiated. Signed and dated written informed consent must be obtained from each subject prior to enrollment into the trial.

All informed consent/assent forms must be approved for use by the sponsor and receive approval from an IRB/IEC prior to their use. If the consent form requires revision (e.g. due to a protocol amendment or significant new safety information), it is the investigator's responsibility to ensure that the amended informed consent is reviewed and approved by the governing IRB/IEC and that it is read, signed and dated by all subjects subsequently enrolled in the trial as well as those currently enrolled in the trial.

#### **11.1.2 Institutional Review Board (IRB) Approval**

This trial is to be conducted in accordance with Institutional Review Board regulations (U.S. 21 CFR Part 56.103). Only an IRB/IEC approved version of the informed consent form will be used.

### **11.2 Ethical Conduct of the Trial**

This trial will be conducted in accordance with the ethical principles that originated with the Declaration of Helsinki.

### **11.3 Subject Confidentiality**

All personal trial subject data collected and processed for the purposes of this trial should be maintained by the investigator and his/her staff with adequate precautions as to ensure

that the confidentiality of the data is in accordance with local, state, and federal laws and regulations.

Monitors, auditors and other authorized representatives of CRO Drug Safety Navigator, the sponsor, the IRB/IEC approving this trial, the FDA, the Department of Health and Human Services, other domestic government agencies, and other foreign regulatory agencies will be granted direct access to the trial subject's original medical and trial records for verification of the data and/or clinical trial procedures. Access to this information will be permitted to the aforementioned individuals to the extent permitted by law.

A report of the results of this trial may be published or sent to the appropriate health authorities in any country in which the IMP may ultimately be marketed, but the subject's identity will not be disclosed in these documents.

## **11.4 Documentation**

Source documents may include a subject's medical records, hospital charts, clinic charts, the investigator's trial subject files, as well as the results of diagnostic tests such as X-rays, laboratory tests, and EKGs. The investigator's electronic copy of the eCRFs serves as the investigator's record of a subject's trial-related data.

### **11.4.1 Retention of Documentation**

All trial related correspondence, subject records, consent forms, record of the distribution and use of all IMP and copies of case report forms should be maintained on file for at least two years after the last approval of a marketing application in an ICH region and until there are no pending or contemplated marketing applications in an ICH region; or until at least two years have elapsed since the formal discontinuation of clinical development of the IMP. These documents will be retained for a longer period if required by the applicable regulatory requirements or by an agreement with the sponsor. It is the responsibility of the sponsor to inform the investigator/institution as to when these documents no longer need to be retained. The investigator must notify the sponsor prior to destroying trial documentation even after the above-mentioned time has passed.

If the responsible investigator retires, relocates, or for other reasons withdraws from the responsibility of keeping trial records, custody must be transferred to a person who will accept the responsibility. The sponsor must be notified in writing of the name and address of the new custodian.

## **11.5 Recording of Data on Source Documents and Electronic Case Reports Forms (eCRFs)**

All subject data will be captured in the subject source documents which will be transcribed to the eCRFs. The investigator is responsible for ensuring that trial data is completely and accurately recorded on each subject's eCRF, source documents, and all trial-related

materials. All trial data should also be attributable, legible, contemporaneous, and original. Recorded data should only be corrected in a manner that does not obliterate, destroy, or render illegible the previous entry (e.g. by drawing a single line through the incorrect entry and writing the revision next to the corrected data). An individual who has corrected a data entry should make clear who made the correction and when, by adding to the correction his/her initials as well as the date of the correction.

Data entry of all enrolled subjects will use software that conforms to 21 CFR Part 11 requirements and will be performed only by staff that have been trained on the system and have access to the system. An audit trail will be maintained within the electronic system to capture all changes made within the eCRF database. After the end of the trial and database lock, compact discs (CDs) containing copies of all applicable subjects' eCRFs will be provided to each investigator site to be maintained on file by the investigator.

### **11.6 Monitoring and Quality Assurance**

During the course of the trial a clinical research associate (CRA) will make routine site visits to review protocol compliance, assess IMP accountability, and ensure the trial is being conducted according to the pertinent regulatory requirements. The review of the subjects' medical records will be performed in a manner that adequately maintains subject confidentiality. Further details of the trial monitoring (including medical monitoring) will be outlined in a monitoring plan.

Domestic and foreign regulatory authorities, CRO Drug Safety Navigator and quality assurance, sponsor and or its designees may carry out on-site inspections and/or audits which may include source data checks. Therefore, direct access to the original source data will be required for inspections and/or audits. All inspections and audits will be carried out with consideration to data protection as well as subject confidentiality to the extent that local, state, and federal laws apply.

